11 STATISTICAL DESIGN AND ANALYSIS

11.1 Statistical Analysis Plans

A detailed Statistical Analysis Plan (SAP) will be finalized prior to study termination.

Descriptive statistics (n, mean, median, standard deviation [SD], minimum, and maximum for continuous data; frequencies and percentages for categorical data) will be used to summarize study data. Unless specified otherwise, all statistical testing will be two-sided and performed using a significance level of 0.05.

11.2 Analysis Populations

The following population will be defined for analysis:

- Safety population: Includes all subjects who receive at least one dose of open-label study treatment and have at least one post-dose visit. Subjects will be analyzed according to the treatment received. This population will be used for all safety and efficacy analyses.

11.3 Determination of Sample Size

In total, approximately 300 subjects are to be enrolled in this study (i.e., both rollover and *de novo* subjects). It is anticipated that approximately 50% of subjects randomized into the double-blind study (Study OS440-3004) may roll over into this open-label study, and US subjects who did not participate in the previous double-blind Study OS440-3004 (i.e., *de novo* subjects) may also enroll into the current study. The number of subjects at each site will be determined primarily by the rate of recruitment in Study OS440-3004. No statistical rationale for subject number is provided.

The sponsor has previously completed a 1-year, open-label safety study (Study OS440-3003) at the 40-mg per day dose. In Study OS440-3003 a total of 148 subjects were treated. Study OS440-3005 is designed to enrich the existing safety database and provide long-term safety and tolerability data at the maximum daily dose of 80 mg/day. Target recruitment includes at least 100 subjects treated at 6 months and 50 subjects treated for 1 year at 80-mg per day.

11.4 Efficacy Analyses

11.4.1 Efficacy Endpoints

11.4.1.1 Patient Global Impression of Change

Descriptive summaries for PGIC scores will be tabulated by study visit and for change from baseline.

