6.2 Baseline – Visit 6 (Final Visit) of Study OS440-3004 (Week 0)

For *de novo* subjects, the following assessments and procedures will be performed at the Baseline visit: assign enrollment number, vital signs, urine pregnancy test, C-SSRS, TNmAS-MAL, PGIC,

USP, dispensing of study medication, recording of AEs and concomitant medications, and scheduling/confirmation of the next study visit.

For Study OS440-3004 subjects willing to continue into this study, Baseline for this study will be conducted at the same time as Visit 6/Day 92 (Final Visit) of Study OS440-3004. All assessments performed at Visit 6/Day 92 (Final Visit) of Study OS440-3004 should not be repeated but should be recorded as the same assessments at Baseline for this study.

At Baseline, the investigator will fully explain to the subject the objectives, characteristics, and procedures for the open-label study. Baseline assessments/procedures will include the following:

- Obtain a signed and dated ICF from each subject prior to any study-specific procedures being conducted ([Section 13.3](#)).
- Assess eligibility according to the inclusion ([Section 5.1](#)) and exclusion criteria ([Section 5.2](#)).
- Assignment of an enrollment number ([Section 7.4](#)).
- Record demographic data, including age, sex, race, and ethnicity.
- Record medical and surgical history ([Section 9.1](#)).
- Record physical examination results ([Section 9.3](#)).
- Record weight and height ([Section 9.4](#)).
- Record vital sign measurements, including blood pressure (BP), heart rate, respiratory rate, and body temperature ([Section 9.2](#)).
- Collect blood and urine samples for hematology, serum chemistry, and urinalysis ([Section 9.5](#)). Subject should be fasting if possible.
- Perform a standard 12-lead electrocardiogram (ECG) ([Section 9.6.1](#)).
- Because contraception is required throughout the study for both males and females, the use of an acceptable method throughout the study will be discussed with all subjects ([Section 7.8](#)).
- Collect a urine sample for pregnancy testing for women of childbearing potential ([Section 7.8](#)).
- Administer the Columbia–Suicide Severity Rating Scale (C-SSRS) ([Section 9.6.3](#)).
- Perform the TNmAS-MAL assessment ([Section 8.2](#)).
- Administer the EDSS assessment ([Section 8.3](#)).
- Administer the PGIC questionnaire ([Section 8.1](#)).
- Administer the USP questionnaire ([Section 9.6.2](#)).

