8 EFFICACY ASSESSMENTS

8.1 Patient Global Impression of Change

The PGIC is a standard instrument that is a well validated outcome measure. The 7-point PGIC measures change in the subject's overall status using the following categorical scale:

- 1 = Very much improved
- 2 = Much improved
- 3 = Improved
- 4 = No change
- 5 = Minimally worse
- 6 = Much worse
- 7 = Very much worse

The PGIC will be completed at the visits specified in Table 1. The PGIC is provided in Appendix 3.

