Appendix 3. Patient Global Impression of Change Scale

PATIENT'S GLOBAL IMPRESSION OF CHANGE (PGIC) SCALE

Date _____ Patient Name _____ Date of Birth _____

Chief Complaint (Presenting Problem): _____

Since beginning treatment at this clinic, how would you describe the change (if any) in ACTIVITY LIMITATIONS, SYMPTOMS, EMOTIONS, and OVERALL QUALITY OF LIFE, related to your painful condition? Please circle the number below, that matches your degree of change since beginning care at this clinic for the above stated chief complaint.

No change	Almost the same	A little better	Somewhat better	Moderately better	Better	A great deal better
1	2	3	4	5	6	7

Explanation:

- 1 = No change (or condition has got worse)
- 2 = Almost the same, hardly any change at all
- 3 = A little better, but no noticeable change
- 4 = Somewhat better, but the change has not made any real difference
- 5 = Moderately better, and a slight but noticeable change
- 6 = Better, and a definite improvement that has made a real and worthwhile difference
- 7 = A great deal better, and a considerable improvement that has made all the difference

[figure not shown]
Patient's signature: X _____

[figure not shown]
Do not write in this box - FOR OFFICE USE ONLY.

[figure not shown]
NOTE TO HEALTH CARE PROVIDER

[figure not shown]
A significant, favorable change is a score of 5- 7
No significant change is a 1-4 response.
Note, this is a dichotomous scale (5-7 = yes; 1-4 = no).
A 2-point change is significant from their last reported score.
Reference: Hurst H, Bolton J. Assessing the clinical significance of change scores recorded on subjective outcome measures. Journal of Manipulative Physiological Therapeutics (JMPT) 2004;27:26-35.

[figure not shown]

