6. The PGIC will not be done at Baseline for *de novo* subjects.
7. At the end of treatment, a 2-week taper period will take place from Weeks 54 to 56. Subjects who discontinue early should also follow the 2-week taper period.

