9.2. Efficacy Analyses

PGIC categories will be summarized by frequencies and percentages by study visit. PGIC will also be summarized using descriptive statistics by study visit.

TNmAS-MAL, TNmAS-TL, and EDSS will be summarized descriptively by study visit in terms of actual values and change from baseline values. In addition to this change from baseline (from Visit 6/ET in OS440-3004), the change from baseline in Study OS440-3004 will be summarized for TNmAS-MAL and TNmAS-TL.

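### The PGIC already rates change, yet the protocol takes it before the first open-label dose and plans change from that rating; the SAP differs, and rollover and de novo subjects share no fixed reference point

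*Protocol*

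**What the plan says.** **Nature of the scale.** Protocol Section 8.1: "The 7-point PGIC measures change in the subject's overall status using the following categorical scale". It gives no reference period and points to Appendix 3 for the form. The Appendix 3 stem reads "Since beginning treatment at this clinic, how would you describe the change (if any", which is the only recall anchor in either document.

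**When it is given.** Protocol Table 1 schedules the PGIC at Baseline for rollover and for de novo subjects, and again at Week 60. Table 1 footnote 1 and Section 6.2 both name it among the few assessments done at the de novo Baseline visit: "urine pregnancy test, C-SSRS, TNmAS-MAL, PGIC". The Section 6.2 procedure list puts it ahead of dispensing and of the first dose given at the site. For rollover subjects, Baseline is the final visit (Visit 6/Day 92) of OS440-3004, whose assessments are carried over. The SAP's schedule differs. Its Table 1 footnote 6 says: "The PGIC will not be done at Baseline for *de novo* subjects". Its Table 1 also keeps a Week 28 PGIC, which Country-Specific Amendment 2 removed for the United States.

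**How it is analysed.** Protocol Section 11.4.1.1: "Descriptive summaries for PGIC scores will be tabulated by study visit and for change from baseline". SAP Section 9.2: "PGIC categories will be summarized by frequencies and percentages by study visit", and "PGIC will also be summarized using descriptive statistics by study visit". The SAP reserves change from baseline for the other endpoints: "TNmAS-MAL, TNmAS-TL, and EDSS will be summarized descriptively by study visit in terms of actual values and change from baseline values". SAP Section 7.2.2 plans no subgroups. SAP Section 3.3 nevertheless says its analyses agree with the protocol's, and SAP Section 3.1 cites Amendment 1 as the reference protocol.

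**The concern.** A rating of change needs a starting point that precedes it and a period of treatment to judge. At Baseline a de novo subject has neither within this study. Any answer then reflects earlier care, or the withdrawal of anti-spasticity medication. A rollover subject's Baseline rating is an end-of-study outcome from a different, placebo-controlled trial. Subtracting either from the Week 60 rating gives a difference between two change ratings, which is not the change since Baseline that the protocol's label suggests.

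The stem adds a second problem that remains when the subtraction is dropped. It is not tied to the first open-label dose. For a rollover subject it may reach back to the start of OS440-3004 or to first care at the site. For a de novo subject it may mean first care at the site or the first AERT dose. Both kinds of subject are pooled in the by-visit summary. At stake is what can be said about PGIC over one year, which is one of three secondary objectives.

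**Working it through.** The plan states no PGIC rate, power or sample size, so there is no figure to reproduce. The check is mainly a comparison of texts, with two small illustrations.

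**1. Protocol against SAP.**

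| Item | Current protocol | SAP |
|---|---|---|
| De novo Baseline PGIC | Done (Table 1, footnote 1, Section 6.2) | Not done (Table 1 footnote 6) |
| PGIC change from baseline | Planned (Section 11.4.1.1) | Not planned (Section 9.2) |
| Week 28 PGIC | Removed by the US-only Amendment 2 | Scheduled (Table 1) |
| Statement on agreement | – | Consistent with the protocol (Section 3.3) |

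De novo subjects can come only from the United States (Protocol Section 5), so the US amendment is the protocol text that applies to them. If the SAP's schedule were followed instead, the protocol's change score could not be computed for any de novo subject. At the SAP's cap (Section 6) that is up to 50 of about 300, or 50/300 = 16.7%. The protocol sets no cap.

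**2. What the subtraction returns.** Change is the post-baseline value minus the baseline value (SAP Section 7.4.1). The ratings here are assumptions on the Section 8.1 scale: every subject rates 2 (much improved) at Week 60, every de novo subject rated 4 (no change) at Baseline, and every rollover subject rated b at Baseline. With w the de novo fraction:

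mean change = w × (2 − 4) + (1 − w) × (2 − b)

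| De novo fraction w | b = 2 | b = 3 | b = 4 |
|---|---|---|---|
| 50/300 = 0.167 | -0.33 | -1.17 | -2.00 |
| 0.25 | -0.50 | -1.25 | -2.00 |
| 0.50 | -1.00 | -1.50 | -2.00 |

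For example, with w = 0.167 and b = 3: 0.167 × (-2) + 0.833 × (-1) = -1.17. The Week 60 ratings are identical in all nine cells. The mean moves from -0.33 to -2.00 solely through the rollover Baseline rating and the mix of subjects.

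**3. Length of the recall period.** Week 60 is 60 × 7 = 420 days after Baseline. A rollover subject who answers from the start of double-blind treatment covers about 420 + 92 = 512 days, and 512/420 = 1.22, or 22% longer. This assumes that anchor and counts Day 92 as 92 days. It shows that the stem permits different periods. It does not estimate a bias.

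**4. Scale direction.** In Section 8.1, 1 is the best category and 7 the worst. In Appendix 3, 1 is no change or worse and 7 is the most improvement. A de novo subject starting at no change could move from -3 to +3 on the first scale (1 − 4 to 7 − 4), but only from 0 to +6 on the second (1 − 1 to 7 − 1), with improvement carrying the opposite sign.

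**The case against.** The strongest reply is that the SAP already omits the change score. Protocol Section 11.1 leaves detail to the SAP, and SAP Section 9.2 gives frequencies and descriptive statistics by visit. A reader might infer from the protocol that a PGIC change from baseline will be reported; the SAP does not support that. What stands is an unreconciled protocol plan and a SAP consistency statement that is wrong for this endpoint.

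Second, a reader might call it a defect that a rollover subject who is much improved at both visits has a change of zero. If both answers share an earlier anchor, zero is a fair description of maintained status, and Appendix 3 itself contemplates comparison with the last score. A stem anchored to the first open-label dose would also lead such a subject to answer no change. That complaint should not be pressed. The de novo Baseline rating, and the mixing of the two groups, are not answered by it.

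Third, the stem belongs to Appendix 3, while the improved-to-worse categories belong to Section 8.1. That is correct, and the conflict between the two scales is a further source of ambiguity. Section 8.1 does name Appendix 3 as the form, so its stem is the one the protocol supplies.

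Fourth, how subjects read the stem is inference, and so is any benefit carried over from OS440-3004, for which neither document gives results. The plain text shows only that the stem is not tied to the first open-label dose.

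Fifth, a single post-dose PGIC cannot be claimed for the whole study, because the removal of Week 28 applies to the United States only.

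**Conclusion.** The point holds in a limited form. The current protocol collects a rating of change before open-label treatment begins, including from de novo subjects with nothing in this study to rate, and plans change from that rating. The SAP contradicts the protocol on both the collection and the analysis while declaring agreement. The only stated reference point is not the first open-label dose and can cover different periods in two groups that are pooled. Dropping the subtraction does not cure this, because the by-visit summary is affected too.

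The consequence is modest. This is a descriptive secondary endpoint in an open-label safety study, and SAP Section 7.4.1 says no statistical tests will be performed. The range of -0.33 to -2.00 rests on assumed Baseline ratings, and the 512 days on assumed recall from the start of the double-blind study. Neither is a prediction. The changes are still worth making, because they alter what is collected and reported and most of them are edits to wording.

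**What to change.** - **Protocol Section 11.4.1.1:** delete the change-from-baseline summary for the PGIC.
- **Protocol Table 1, footnote 1 and Section 6.2:** remove the PGIC from the de novo Baseline visit, to match the SAP.
- **Rollover Visit 6 PGIC:** label it an OS440-3004 outcome and do not use it as a baseline.
- **SAP Section 9.2:** report post-dose PGIC category frequencies separately for rollover and de novo subjects.
- **SAP Sections 3.1 and 3.3:** cite the current protocol version, including the US amendment, and correct the consistency statement. State which PGIC visits apply inside and outside the United States.
- **Section 8.1 and Appendix 3:** adopt one PGIC version with one scale direction and one stated reference point, such as the first open-label dose.

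The cost is one line on the form, one questionnaire fewer at one visit, one additional split in a table, and edits to wording. The real downside lies in the stem. Changing it during the study is worthwhile only if ratings collected under the current stem are kept apart and shown separately, which leaves fewer subjects under each. If the stem cannot be changed, the other edits still help, and the report should state that the recall period is not anchored to the open-label year.

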11.4.1.2 Total Numeric-Transformed Modified Ashworth Scale

Descriptive summaries for TNmAS-MAL scores will be tabulated by study visit and for change from baseline.

11.4.1.3 Expanded Disability Status Scale

Descriptive summaries for EDSS scores will be tabulated by study visit and for change from baseline.

11.5 Safety Endpoints

Safety endpoints will be reported on the Safety population. Subjects will be reported according to the treatment they actually received. Safety assessment will be based on descriptive statistics and individual subject listings. No statistical tests will be performed for any of the safety assessments.

All reported AEs will be mapped to the Medical Dictionary for Regulatory Activities (MedDRA) system organ classifications (SOCs) and preferred terms (PTs). If a subject reports multiple events of a single PT, the greatest severity and strongest investigator assessment of relationship to study treatment will be assigned to that PT. Should an event have a missing severity or relationship, it will be classified as having the highest severity and/or strongest relationship to study drug. Summaries of treatment-emergent AEs (TEAEs) will include any AEs reported beginning with the first dose of study treatment on Day 1. The occurrence of TEAEs will be summarized by treatment group using SOCs, PTs, and severity. Separate summaries of treatment-emergent SAEs, TEAEs considered related to study treatment, and events leading to the discontinuation of study drug will be generated.

Descriptive summaries of vital signs, clinical laboratory results, USP results, and the C-SSRS results will be presented by study visit and treatment group. The number and percentage of subjects with treatment-emergent clinical laboratory abnormalities will be summarized by treatment group. Normal range clinical laboratory shifts from baseline to end of study will be summarized by treatment group.

Concomitant medications will be coded using the World Health Organization (WHO) dictionary. These data will be summarized by treatment group. Previous and concomitant medications will be presented in a data listing.

Subject disposition will be presented for all subjects. The numbers of subjects who complete the study and who discontinue early from the study will be provided. The reasons for early discontinuation will also be presented.

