4.2 Rationale for Study Design and Dose Selection

Chronic exposure in an open-label extension design is appropriate to evaluate the safety of long-term use of an investigational product. The omission of a control group is appropriate. The subjects will be selected according to predefined entry criteria from the previous Phase 3, randomized, multicenter, double-blind, placebo-controlled study. The open-label study treatment duration of approximately 1 year is adequate for chronic exposure. Nonclinical arbaclofen data from a 3-month rat toxicity study (Study 0460RO24.001) show margins of exposure greater than 1 and adverse effects at exposures up to 10-fold higher than those projected to occur in this Phase 3 study that were not life-threatening, were clinically monitorable, and were reversible, which

supports a dose level of 80 mg. To date, Osmotica has conducted 11 clinical studies (Phases 1 through 3) utilizing AERT in doses up to 80 mg/day in single and divided doses.

The open-label extension study is necessary to obtain safety information about the long-term use of AERT at the highest target dose to treat patients with spasticity due to MS because it is a chronic condition.

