Note: For *de novo* subjects being considered for enrollment, a Screening visit should occur a maximum of 21 days prior to Baseline to allow for any concomitant medication wash-out required for Inclusion Criterion 6. For *de novo* subjects, only the following assessments and procedures will be performed at the Baseline visit: assign enrollment number, vital signs, urine pregnancy test, C-SSRS, TNmAS-MAL, PGIC, USP, dispensing of study medication, recording of AEs and concomitant medications, and scheduling/confirmation of the next study visit.

2. If a subject prematurely withdraws from the study, the subject should taper from study medication as described in Section 7.1 and all evaluations described under Visit 8/Week 60 (Final Visit) must be performed.
3. Vital signs will be measured with the subject in a supine position and in a standing position 3 minutes after the supine assessment is completed. Body temperature and respiratory rate will be measured only during the supine assessment.
4. For *de novo* subjects, premenopausal women of childbearing potential must have a negative serum pregnancy test within 21 days before Baseline. Urine pregnancy testing will be performed for all female subjects at the other visits as noted.
5. The TNmAS-MAL assessment will be performed prior to any scheduled laboratory draws. The most affected limb will be determined by the investigator.
6. At the end of treatment, a 2-week taper period will take place from Weeks 54 to 56. Subjects who discontinue early should also follow the 2-week taper period.

Figure 1: Timeline Diagram, Study OS440-3005

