7.1.1 Treatment Administration

The study medications will be administered orally twice daily (every 12 hours, or BID) without regard to food. Note: For the 60 mg/day titration, this means 1 x 20 mg AERT in the morning and 2 x 20 mg AERT in the evening.

Once the subject has reached the maintenance dose, they will remain on that dose for approximately 1 year. The maintenance dose will be the highest tolerated dose, not exceeding 80 mg per day. All attempts should be made for subjects to titrate to the 80 mg per day dose. If subjects experience untoward tolerability issues due to AERT, they may taper study drug only under the guidance of the study site (i.e., in 20 mg increments per week). Subjects may subsequently attempt study drug taper if the investigator deems this clinically appropriate. There will be no taper phase for subjects who solely achieve a 40 mg per day maintenance dose. Subjects may attempt to titrate to the target dose of 80 mg per day, if tolerability issues have resolved.

If a subject misses 7 or more consecutive days of dosing AND has taken less than 80% of their doses of study medication in a 42-day (6-week) period, then the subject must be discontinued (see [Section 12.4](#)).

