7.3. Management of Analysis Data

7.3.1. Data Handling

Unscheduled or repeated laboratory results will not be analyzed for the summary of continuous values but will be included in the laboratory shift tables as follows. Unscheduled tests will be included with the time of the nearest regularly scheduled test. If there is a scheduled test and one or more unscheduled tests assigned to the same time point, the most conservative test (i.e., a test with low or high results) will be used. Repeated tests will be included only if they reflect abnormal (low or high) results and the corresponding original results are normal. All laboratory values, for all visits, will be provided in by subject listings.

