10.3. Clinical Laboratory Evaluations

Clinical Laboratory results will be summarized descriptively by time point for the observed value as well as for the change from baseline value. In addition, laboratory shift tables will be provided for all laboratory parameters where low/normal/high or abnormal/normal status can be ascertained. Listings of individual laboratory parameters by visit with normal ranges and abnormality assessments will also be completed by subject.

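### The protocol's laboratory shift ends at an off-drug sample, the SAP implies a different shift and drops the treatment-emergent abnormality count, so no SAP table says how many subjects had an on-treatment abnormality

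*Protocol*

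**What the plan says.** Protocol Section 11.5 plans three laboratory displays:

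- By visit: "Descriptive summaries of vital signs, clinical laboratory results, USP results, and the C-SSRS results will be presented by study visit and treatment group".
- A subject count: "The number and percentage of subjects with treatment-emergent clinical laboratory abnormalities will be summarized by treatment group".
- A shift: "Normal range clinical laboratory shifts from baseline to end of study will be summarized by treatment group". The section does not define the end of study.

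Protocol Table 1 and Section 6.6 put the last laboratory sample at Visit 8, Week 60. On the end of dosing, the Table 1 footnotes say: "At the end of treatment, a 2-week taper period will take place from Weeks 54 to 56". Section 7.1.1 adds: "There will be no taper phase for subjects who solely achieve a 40 mg per day maintenance dose".

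SAP Section 10.3 plans observed values and changes by time point, subject listings, and shifts: "laboratory shift tables will be provided for all laboratory parameters where low/normal/high or abnormal/normal status can be ascertained". It names no post-baseline visits and has no count of subjects with treatment-emergent abnormalities. SAP Section 7.3.1 says how extra results enter the shift tables: "Unscheduled tests will be included with the time of the nearest regularly scheduled test". Where several results share a time point, the abnormal one is preferred. The same section keeps unscheduled and repeat results out of the continuous summaries. SAP Section 7.3.3 assigns early-termination data to the nearest scheduled visit, or to the next available one if that visit already has data. SAP Section 3.3 reports no departure from the protocol's analyses.

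**The concern.** Long-term safety is the primary objective, and laboratory tests are a listed safety endpoint. The question for a laboratory table is how many subjects moved outside the normal range while taking the drug. A shift that ends weeks after the last dose answers a different question: how many are still abnormal after stopping.

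The SAP does not settle the matter. Its handling rules point to a by-visit shift, its analysis section lists no visits, and its consistency statement points back to the protocol's single shift. Two programmers could build different tables and each cite the documents. The one protocol display that counts subjects with a treatment-emergent abnormality is absent from the SAP.

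**Working it through.** The plan gives no figure to reproduce. The check is arithmetic on the visit schedule, then a comparison of the planned displays.

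**1. Time off drug at the final sample.** Inputs: taper Weeks 54 to 56 (Protocol Table 1 footnote 6); Visit 8 at Week 60 ±3 days and Visit 7 at Week 56 ±5 days (Table 1); no taper for 40 mg-only subjects (Section 7.1.1).

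- Taper length: 56 − 54 = 2 weeks, as stated.
- Tapered completers: 60 − 56 = 4 weeks = 28 days. With the Visit 8 window, 28 ± 3 = 25 to 31 days. If the Week 56 window also moves the last dose, 28 ± 8 = 20 to 36 days.
- 40 mg-only completers: 60 − 54 = 6 weeks = 42 days.

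**2. Draws used.** Protocol Table 1 schedules six post-baseline draws, at Weeks 6, 14, 28, 42, 54 and 60. Five are on drug and one is off drug. A completer's shift from baseline to Week 60 uses 0 of the 5 on-drug draws. (SAP Table 1, as it reads in the available copy, also marks a draw at the Week 56 telephone visit. The protocol does not, and the two schedules should be reconciled.)

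**3. Planned displays side by side.**

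| Display | Protocol 11.5 | SAP | Counts subjects with any on-treatment abnormality? |
|---|---|---|---|
| Continuous summaries by visit | Yes | 10.3, without unscheduled or repeat results | No |
| Shift table | Baseline to end of study | 10.3 names no visits; 7.3.1 implies scheduled time points | No |
| Treatment-emergent abnormality count | Yes | Absent | Yes, but only in the protocol |
| Listings | Individual listings | All values | Not a summary |

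**4. Why by-visit shifts do not replace the missing count.** Let a₁ to a₅ be the numbers of subjects abnormal at the five on-drug visits. The number abnormal at least once lies between max(aₖ) and the smaller of N and a₁ + … + a₅. If the five counts are equal to a, the answer lies anywhere from a (the same subjects each time) to 5a (different subjects each time, if 5a ≤ N). By-visit tables cannot say which, so the subject-level count is uncertain by a factor of up to five.

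**5. Early termination.** The protocol asks early withdrawers both to taper over 2 weeks and to have the Visit 8 evaluations, so the sample may be taken on or off drug. As an assumed example, take a last dose at Week 38, a sample at Week 40 and no Week 42 visit. The distances are 42 − 40 = 2 weeks and 40 − 28 = 12 weeks, so SAP 7.3.3 puts this off-drug value in the Week 42 column, an on-drug visit for everyone else.

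**6. Illustration only.** The documents give no recovery rate. If abnormalities present at the last dose resolved exponentially with a mean of 1, 2 or 4 weeks, the share still visible 4 weeks later would be exp(−4/1) = 2%, exp(−4/2) = 14% or exp(−4/4) = 37%. This shows the direction and possible range of the loss in the protocol's shift table. It is not an estimate for this drug.

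**The case against.** The strongest reply is that the end-of-study shift was never meant to work alone. The sentence before it in Protocol 11.5 plans the treatment-emergent count, and results are also summarised by visit. A reader might infer that on-drug abnormalities are lost from the reporting altogether. The documents do not support that: by-visit summaries and full listings remain, and the monitoring board follows clinically important laboratory values.

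A reader might also infer that the SAP's shift tables have no time points. That goes too far. The rule in 7.3.1 makes sense only for tables by scheduled test, and it already favours abnormal results. What is missing is a list of visits and a worst on-treatment category. Nor are drop-outs automatically pooled at Week 60, because 7.3.3 moves them to the nearest visit.

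Finally, Protocol Section 4.2 says that adverse effects "were clinically monitorable, and were reversible". It is tempting to read this as evidence that laboratory changes would vanish before Week 60. The statement concerns a 3-month rat study, does not say the effects were laboratory changes, and gives no time to recovery in patients. It makes reversibility plausible and no more.

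Three things stand after this. The reply leans on the treatment-emergent count, which the SAP does not carry over. Unscheduled results reach a summary only through the shift tables, so under the protocol's shift an unscheduled on-drug abnormality would appear only in listings. Adverse event tables do not close the gap either: Protocol Section 9.5 makes an abnormal value an adverse event only when it is clinically significant and needs treatment or leads to discontinuation.

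**Conclusion.** The concern holds in a limited form. The protocol's shift, read as baseline to Week 60 for completers, is measured about 4 weeks after the last dose (about 6 weeks without a taper) and uses none of the five on-drug draws. The SAP implies a different shift, names no visits and omits the protocol's subject count, while stating that nothing has changed. The practical gap is that no SAP table gives, per subject, whether any on-treatment abnormality occurred. By-visit counts leave that number open by a factor of up to five. Early-termination samples can also blur on-drug and off-drug values.

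This rests on reading end of study as Visit 8, which is natural for completers but not stated, and on the protocol's visit schedule. It does not rest on any assumed abnormality or recovery rate. It is a gap in the summary of the primary safety data, worth closing before database lock. It is not evidence that laboratory safety goes unmonitored.

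**What to change.** In Protocol 11.5 and SAP 10.3:

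- Make the main shift table baseline to worst on-treatment value, from first to last dose and including unscheduled tests. This matches the treatment-emergent window in SAP 10.1.
- Keep shifts by visit and name the visits: Weeks 6, 14, 28, 42 and 54.
- Show Week 60 and any other sample after the last dose separately, labelled post-treatment. Apply this before the visit assignment in SAP 7.3.3, so that an off-drug early-termination sample cannot enter an on-drug column.
- Restore the count of subjects with treatment-emergent laboratory abnormalities and define it, for example as within range at baseline and outside it at any on-treatment test.
- Define end of study wherever the term is kept.
- Correct SAP 3.3 so that it records any remaining difference from the protocol.

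The cost is wording and one or two extra tables. No new samples are needed, and the dosing dates required to classify each sample are already to be listed under SAP 8.6.
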